#### **11.4.1. Definition of Dose-limiting Toxicity**

Dose-limiting toxicity (DLT) will be defined using the NCI Common Toxicity Criteria (CTC) (Version 4). Any Grade 3 or any Grade 4 toxicity that is not reversible within 2 weeks, or any life-threatening event, or treatment-related death will be considered a DLT. Any grade 2 or higher serious autoimmune toxicities particularly those affecting vital organs (e.g. cardiac, renal, CNS) will be considered a DLT if it occurs within 2 weeks with or without treatment. Exceptions to these DLT's are as follows:

- Events associated with the biopsy procedure/catheter placement: seizures or hemorrhages occurring during anesthesia or the biopsy/catheter insertion proper prior to administration of the agent if Grade 2 or lower (Grade 3 or higher surgical complication from insertion of catheter is considered DLT).
- Seizures: Due to the nature of the disease under investigation in this protocol, patients may have pre-existing seizures or be susceptible to new seizures as a result of the underlying disease process. Although seizures may be defined as Grade 3 or 4 toxicities under NCI CTC, and will be reported as such in this protocol, seizures will not be considered DLT if, in the opinion of the Principal Investigator they have not increased in frequency or can be attributed to another recognized cause of increasing seizure frequency such as sub-therapeutic anti-convulsant levels or biopsy proven tumor progression.
- New neurologic deficits: Due to the nature of the disease under investigation in this protocol, patients may develop new neurologic deficits as a result of tumor invasion. A new neurologic deficit, which resolves within 2 weeks after initiation of medical therapy, will not be considered a DLT. Similarly, late (≥ 4 weeks after completion of infusion) DLTs thought to be drug or procedure related, which resolves within 2 weeks after initiation of medical therapy, will not be considered a DLT. New neurological symptoms will not be a DLT if they can be ascribed to tumor

progression (e.g. documented with histopathologic analyses of biopsy tissue; or; they respond to treatment (e.g. oral steroids, within 2 weeks)).

- Thromboembolism: Due to the high incidence of deep vein thrombosis (DVT) in this patient population, patients may have undiagnosed pre-existing DVTs or be susceptible to the development of DVTs due to the underlying disease process. Although DVT may be defined as Grade 3 or 4 toxicities under NCI CTC, and will be reported as such in this protocol, DVT will not be considered DLT in this protocol.
- Syndrome of Inappropriate Antidiuretic Hormone (SIADH): Due to the high incidence of SIADH in this patient population, patients may be susceptible to the development of SIADH due to the underlying disease process. Although SIADH may be defined as Grade 3 toxicity under NCI CTC, and will be reported as such in this protocol, SIADH will not be considered DLT in this protocol unless it is refractory to medical management.
- Muscle Weakness and Weight Gain: Due to the high incidence of muscle weakness and weight gain in patients taking steroids in this patient population, patients may be susceptible to the development of muscle weakness or weight gain which is due to steroids alone. Although muscle weakness may be defined as Grade 3 or Grade 4 toxicity and weight gain ≥ 20% may be defined as Grade 3 toxicity under NCI CTC, and will be reported as such in this protocol, muscle weakness or weight gain will not be considered DLT in this protocol if the patient has required steroids greater than physiologic doses in the interval between the immunization and the development of the toxicity.
- Tumor Progression: Due to the nature of the disease under investigation in this protocol, patients may have an increase in pre-existing neurologic deficits or have an onset of new neurologic deficits due to tumor progression. Although such neurologic deficits may be defined as DLTs under NCI CTC, and will be reported as such in this protocol, these clinical changes are not an unexpected phenomenon in this disease in the setting of tumor growth. As a result, neurologic deficits will not be considered a DLT if unequivocal tumor progression can be documented radiographically or histologically.

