#### 11.3. HISTORICAL MODIFICATIONS TO THE PROTOCOL

#### 11.3.1. Study Design Modifications (11/15/2013 AMD025)

As of 11/15/2013, 4 patients have been treated on dose level 5. One patient experienced a DLT upon removal of the treatment catheter. The remaining 3 patients have not experienced a DLT; however, all 3 have had difficulties tapering off steroids. To address this concern, the study is amended to reduce the dose for the next cohort of patients to dose level 2. Up to 6 patients will be accrued at dose level 2. If 2 of these patients experience a DLT as defined in section 11.4, accrual will be suspended. Following a two-week observation period, during which the patient will be evaluated in clinic on day 7 ( $\pm$  2 days) and day 14 ( $\pm$  2 days), a patient summary will be prepared and submitted to the DSMB chair for approval. Once approval from the DSMB chair has been obtained, treatment of the next patient will be allowed. Only one patient will be treated every 2 weeks and there will be only one PVSRIPO treatment per patient without specific approval for a second or more treatments from the FDA and the IRB.

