### **11.4. DOSE-LIMITING TOXICITY**

Patients will be monitored for toxicity indefinitely or until confirmation of recurrent disease or the patient prematurely discontinues from the study at Duke University Medical Center. Adverse events will be categorized and graded in accordance with the NCI CTC (Version 4).

During the dose escalation phase of this study, patients were also monitored for dose-limiting toxicity (DLT). As no patient experienced a DLT on dose level 2, dose level 2 was determined to be the MTD. On 10/06/2014, the protocol was amended to reduce the dose to dose level -1 (see section 11.3.3). Since dose level 2 was determined to be the MTD, DLT monitoring was discontinued at that time.

With the removal of oversight by the study-specific DSMB, a patient summary with toxicity review will no longer need to be generated after each patient (see section 11.3.9).

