#### 11.4.2. Management of Toxicities

If a Grade 3 or 4 NCI CTC toxicity is observed, the patient will be monitored until the NCI CTC toxicity improves to a Grade 1. If this resolves within 4 weeks with or without treatment, these toxicities will not be considered dose limiting. If a new Grade 3 or 4 NCI CTC toxicity is seen again in the same subject after initial resolution within 4 weeks of the initial infusion, a DLT will be declared.

If Grade 2 or higher serious autoimmune NCI CTC toxicity is observed the patient will be monitored until the NCI CTC toxicity improves to a Grade 1. If resolution to Grade 1 occurs within 4 weeks with or without treatment, these toxicities will not be considered dose limiting.

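### Sections 11.4.1 and 11.4.2 set different resolution periods (2 and 4 weeks) for the same dose-limiting toxicities, and 11.5 takes its monitoring definition from the section that omits life-threatening events

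*Combined protocol and SAP*

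**What the plan says.** Section 11.4.1, which is headed as the definition, counts as dose limiting "Any Grade 3 or any Grade 4 toxicity that is not reversible within 2 weeks". It also counts any life-threatening event and any treatment-related death. A serious autoimmune toxicity of Grade 2 or higher "will be considered a DLT if it occurs within 2 weeks with or without treatment". A list of exceptions follows: procedure-related events, seizures, new neurologic deficits, thromboembolism, SIADH, steroid-related weakness or weight gain, and tumor progression. None of them is a general allowance for toxicity that resolves within 4 weeks.

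Section 11.4.2, headed as management, covers the same toxicities. For Grade 3 or 4: "If this resolves within 4 weeks with or without treatment, these toxicities will not be considered dose limiting". For serious autoimmune toxicity of Grade 2 or higher: "If resolution to Grade 1 occurs within 4 weeks with or without treatment, these toxicities will not be considered dose limiting". Its only sentence that declares a DLT concerns a repeat, where a new Grade 3 or 4 toxicity "is seen again in the same subject after initial resolution within 4 weeks of the initial infusion, a DLT will be declared".

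The rules that use the definition do not choose between the two sections during escalation. The dose level 2 rule in 11.3.1 reads "If 2 of these patients experience a DLT as defined in section 11.4, accrual will be suspended", and the discontinuation criterion in 11.8 likewise cites 11.4 as a whole. The MTD rests on the resulting count: "As no patient experienced a DLT on dose level 2, dose level 2 was determined to be the MTD" (11.4). For monitoring after escalation, 11.5 does choose. It names 11.4.2 as the source of its definition of unacceptable toxicity and suspends accrual at 25% or more. Section 11.6 applies the same guideline to second infusions.

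**The concern.** The primary objective is the MTD, and the MTD was declared from a count of zero DLTs at level 2. If two sections of the same protocol classify the same event differently, the reader cannot tell which rule produced that zero or whether the other would have given the same answer.

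The second problem is still active. Section 11.5 points to a section that mostly says when a toxicity is not dose limiting. It gives no positive criterion for autoimmune events, and it omits the life-threatening-event criterion of 11.4.1. Section 16.6 says that new enrolment closed in June 2017 but that selected patients are being retreated, now with lomustine added (11.2.2). The guideline that watches over those patients is the one with the incomplete definition.

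**Working it through.** The plan gives no figure to reproduce. The check is to classify the same event under each section. Days are counted from infusion, with 2 weeks = 14 days and 4 weeks = 28 days. Neither section states when its period starts, so both starting points are tried.

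**Rules applied**

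- 11.4.1, Grade 3/4: DLT if not reversed within 14 days.
- 11.4.1, autoimmune, as written: DLT if onset is by day 14. Read as a slip for non-resolution: DLT if not resolved within 14 days.
- 11.4.2, both kinds: not dose limiting if resolved within 28 days.

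**Main case: onset day 3, Grade 1 by day 21**

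Duration from onset is 21 − 3 = 18 days. Time from infusion to resolution is 21 days.

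| Rule | From onset | From infusion |
|---|---|---|
| 11.4.1 autoimmune, as written | onset day 3 ≤ 14: DLT | onset day 3 ≤ 14: DLT |
| 11.4.1 autoimmune, as non-resolution | 18 > 14: DLT | 21 > 14: DLT |
| 11.4.1 Grade 3/4 | 18 > 14: DLT | 21 > 14: DLT |
| 11.4.2 | 18 ≤ 28: not dose limiting | 21 ≤ 28: not dose limiting |

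The conflict does not depend on the starting point or on how the autoimmune clause is read.

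**Where the conflict stops**

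- Excepted toxicities. A Grade 3 deep vein thrombosis from day 3 to day 21 is removed from DLT by the thromboembolism exception in 11.4.1 and is not dose limiting under 11.4.2. The sections agree.
- Autoimmune, day 10 to day 21. Duration is 21 − 10 = 11 days. This is a DLT if the 11.4.1 clause is taken literally, but not if it means non-resolution counted from onset (11 ≤ 14). The conclusion does not rest on this case.
- Grade 2 autoimmune, day 20 to day 50. Duration is 50 − 20 = 30 days. It falls outside the literal 11.4.1 window, and 11.4.2 would make it a DLT only by implication (30 > 28). The conclusion does not rest on this case either.

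**Monitoring under 11.5**

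Take a life-threatening Grade 4 event that resolves within 4 weeks. Under 11.4.1 it is a DLT in its own right. Under 11.4.2 it is not dose limiting, so it adds nothing to the numerator of the 25% guideline.

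**How much one event could matter**

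Section 11.3.3 gives 7 on-protocol patients at level 2, with no DLT reported. One reclassified event would make the stated basis for the MTD untrue. Two in the cohort of up to 6 would have met the suspension rule in 11.3.1. At level 5, 1 DLT in 4 patients is 25%, above the 20% limit in 11.1.5.1; 0 in 4 is 0%. Of that event the plan says "One patient experienced a DLT upon removal of the treatment catheter". Its duration is not given, so its status under each rule cannot be checked. No autoimmune event or event dates are reported at any level, so the number reclassified cannot be computed.

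**The case against.** Four points can be made on the other side.

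First, the autoimmune clause is probably a drafting slip. The phrase about treatment is the one that 11.4.2 attaches to resolution, so the author may have meant non-resolution within 2 weeks. That is likely right, but it leaves 2 weeks against 4.

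Second, the conflict between the sections is largely historical. DLT monitoring ended with the amendment of 10/06/2014, the level 2 cohort is complete, and the DLT criterion in 11.8 is confined to escalation. This stands. The conflict bears on how past events were classified, and so on how the MTD is reported.

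Third, 11.5 does choose a section, so the monitoring rule is not left without one. This also stands. For monitoring, the fault is a wrong or incomplete cross-reference. Section 11.5 was added after escalation ended, so its choice does not settle which rule applied then.

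Fourth, there are backstops. Section 11.5 also allows suspension for other safety concerns and requires a six-monthly review. Section 11.8 lists two or more Grade 4 events, or any death, possibly related to the agent. Section 16.6 describes adverse-event review weekly on average, and the DSMB-Plus. These lower the risk that a serious event goes unnoticed. They do not correct the count that drives the 25% guideline.

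A reader might go further and infer that a DLT at level 2 was missed or that the MTD is wrong. The documents do not support that. They identify no event whose status changes, and the later dose changes turned on steroid need, inflammation and bevacizumab use (11.3.3, 11.3.5, 11.3.8, 11.3.11), not on DLT counts.

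**Conclusion.** The two sections conflict in the current text. The conflict covers serious autoimmune toxicity of Grade 2 or higher, and Grade 3/4 toxicity outside the 11.4.1 exceptions, when the event starts early and resolves between 2 and 4 weeks. No precedence is stated for the escalation rules. Separately, the definition that 11.5 and 11.6 use has no positive autoimmune criterion and leaves out life-threatening events that resolve within 4 weeks.

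The effect on the declared MTD is unknown and may be nil. The choice of dose level -1 is not affected. The classification rests on the text of the two sections alone. The monitoring conclusion assumes that 11.5 is followed as written, without reading the 11.4.1 criteria into it. The point merits a short amendment and a transparent recount; it does not show that the dose finding failed.

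**What to change.** Make 11.4.1 the single governing definition. A serious autoimmune toxicity of Grade 2 or higher, or a Grade 3 or 4 toxicity, is a DLT if it has not resolved to Grade 1 or lower within 2 weeks of onset, whether or not it was treated. Two weeks is the period already in the section headed as the definition, and its new-neurologic-deficit exception also uses 2 weeks.

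- Align the 4-week sentences in 11.4.2 with this rule, or delete them.
- Keep every exception in 11.4.1, the rule that a Grade 3 or higher catheter-insertion complication is a DLT, the life-threatening-event and treatment-related-death criteria, and the repeat Grade 3/4 DLT now in 11.4.2.
- Change the reference in 11.5, and so in 11.6, from 11.4.2 to 11.4.1, with onset at any time for monitoring.
- Because the escalation events are already known, report the level 2 and level 5 DLT counts under both the 2-week and the 4-week rule, so that the result does not rest on a period chosen afterwards.

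The cost is a short wording amendment and a small reclassification of adverse events already collected. The reported DLT or unacceptable-toxicity counts may change. If nothing moves, the MTD statement is stronger for having been checked.

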#### 11.3.3. Study Design Modifications (10/06/2014 AMD048)

As of 10/06/2014, 7 subjects have been treated on protocol at dose level 2. One additional subject has been treated under a Single Subject Emergency Use Request at dose level 2. Of these eight subjects, six subjects had difficulty or remained unable to be tapered off steroids more than three months post infusion (three subjects required the addition of bevacizumab to facilitate the taper down or off steroids). We are amending the study to reduce the dose to dose level -1 (5.0 X  $10^7$  TCID50) with the goal of limiting the occurrence of known possible side effects of prolonged steroid use in patients who otherwise benefit from this investigational therapy. This dose reduction will allow continued patient accrual and garner more information about patient safety and optimal dosing while the singleinstitution phase 2 study is being developed and reviewed by various regulatory bodies. Our last amendment allowed the enrollment of up to 18 patients, one patient was enrolled under that amendment and thus, we are planning to enroll up to 17 patients on dose level -1. After each patient has been followed for a one-week observation period, during which the patient will have been evaluated in clinic on day 7 (± 2 days), a patient summary will be prepared and submitted to the DSMB chair for approval. Once approval from the DSMB chair has been obtained, treatment of the next patient will be allowed. We will treat up to four subjects within a 30-day period as allowed by DSMB chair, and there will be only one PVSRIPO treatment per patient without specific approval for a second or more treatments from the FDA and the IRB.

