#### 15.2.7. Cerebral Edema and Increased Intracranial Pressure

Cerebral edema may be secondary to the disease process itself, the surgical procedure, necrosis from previous radiation, or inflammation due to immune infiltration of the brain or destruction of tumor cells. Symptoms may include, but are not limited to, severe headache,

confusion, lethargy, unresponsiveness, coma, or focal neurological deficits. Patients will be monitored throughout the course of the study and upon any signs or symptoms of cerebral edema, may have their steroid doses increased or receive treatment with an osmotic diuretic, or surgical decompression. Edema that fails to respond to aggressive therapy may lead to permanent neurological impairment. The probability of this risk can be predicted to some degree based upon tumor size, location, pre-operative neurological impairment, and post-operative course prior to virus administration.

**Special consideration:** In the event a patient demonstrates neurologic or radiographic signs suggestive of an inflammatory reaction secondary to the immune response expected from PVSRIPO for which it would be considered to increase dexamethasone above 4 mg a day after the first 2 weeks post PVSRIPO infusion, dexamethasone will not be increased any further. Instead, patients will be initiated on bevacizumab 7.5 mg/kg IV every 3 weeks and imaged with an MRI after 3 doses (every 9 weeks +/- 2 weeks) to assess if continued utilization of bevacizumab to control the cerebral inflammation is needed. Bevacizumab will not be provided by the study. Every attempt should be made to discontinue dexamethasone. Once patients start bevacizumab, the follow-up visit schedule will be adjusted to coincide with the timing of the bevacizumab instead of the prior PVSRIPO infusion. Therefore, patients will return approximately every 9 weeks for an evaluation with MRI.

If there are adverse events or other circumstances prohibiting the use of bevacizumab, we will use corticosteroids or surgery, or other interventions deemed more appropriate for the patient by the treating physician, if needed, to treat the inflammatory reaction secondary to PVSRIPO.

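### Section 11.4.1 lets a mere response to oral steroids exempt a new neurological deficit from DLT as tumor progression, in conflict with the protocol's own stricter tests

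*Combined protocol and SAP*

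**What the plan says.** Section 11.4.1 (Definition of Dose-limiting Toxicity) sets the base rule for what counts as dose limiting: "Any Grade 3 or any Grade 4 toxicity that is not reversible within 2 weeks, or any life-threatening event, or treatment-related death will be considered". Next comes a list under "Exceptions to these DLT's are as follows", so each bullet overrides the base rule.

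The bullet on new neurologic deficits contains two relevant tests. The first is "A new neurologic deficit, which resolves within 2 weeks after initiation of medical therapy, will not be considered a DLT". The last sentence excuses new symptoms attributable to tumor progression and gives as examples that this is "documented with histopathologic analyses of biopsy tissue; or; they respond to treatment (e.g. oral steroids, within 2 weeks".

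A later bullet in the same section, Tumor Progression, covers the same attribution in stricter terms: "neurologic deficits will not be considered a DLT if unequivocal tumor progression can be documented radiographically or histologically".

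Section 11.4.2 (Management of Toxicities) uses a different window. A Grade 3 or 4 event is followed until it improves to Grade 1 and is not dose limiting if it resolves within 4 weeks.

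Section 11.4 reports the result: "As no patient experienced a DLT on dose level 2, dose level 2 was determined to be the MTD". Section 11.5 then sets a pause at 25% of patients with an unacceptable toxicity at levels -1 and -2, and takes its definition from section 11.4.2. Section 11.6 extends the section 11.5 guideline to retreatment.

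**The concern.** A response to steroids is used as evidence of tumor progression, although the protocol gives reasons why it cannot serve as such. Section 15.2.7 anticipates "neurologic or radiographic signs suggestive of an inflammatory reaction secondary to the immune response expected from PVSRIPO". It also lists immune inflammation among the causes of cerebral edema, for which steroid doses may be raised. Section 13.1 says that inflammation and progression are hard to tell apart.

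*Respond* is also a lower bar than *resolve*. The clause states no degree, grade or duration of response, and needs neither a scan nor tissue. The exemption can thus remove a neurological toxicity that may be caused by the agent and record it as disease.

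The primary objective is to determine the MTD and the phase II dose, and the MTD statement rests on a zero DLT count at level 2. A rule that can hide events from that count bears directly on the statement.

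**Working it through.** The protocol states no operating characteristics for its DLT rules, so there is no figure to reproduce. The check sets the clauses side by side.

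| Place | What excuses the event | Window | Evidence required |
|---|---|---|---|
| 11.4.1, base rule (Grade 3 or 4) | reversal | 2 weeks | course of the event |
| 11.4.1, New neurologic deficits, first test | resolution on medical therapy | 2 weeks | course of the event |
| 11.4.1, New neurologic deficits, last sentence | attribution to progression | 2 weeks (for response) | biopsy tissue, or a response of unstated degree |
| 11.4.1, Tumor Progression | unequivocal progression | none | scan or tissue |
| 11.4.2 | resolution, with follow-up to Grade 1 | 4 weeks | course of the event |

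**Test case.** Take a Grade 3 deficit that starts in week 1, improves somewhat on oral steroids, and is still Grade 3 after 4 weeks, with no scan or tissue showing progression.
- Base rule: a DLT.
- First neurologic test: not excused, because it has not resolved.
- Tumor Progression bullet: not excused, because nothing is documented.
- Section 11.4.2: not excused, because it has not resolved within 4 weeks.
- Last sentence of the neurologic bullet: can be excused, because it responded.

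Only the contested clause releases this event.

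**Effect on the level 2 count.** Section 11.3.1 suspends accrual if 2 of up to 6 level 2 patients have a DLT as defined in section 11.4, so the clause governed that count. By section 11.3.3, 7 patients had been treated on protocol at level 2 when the dose was reduced. The reported count is 0 of 7. One re-scored event would give 1/7 = 14% and remove the stated basis for the MTD. Two would give 2/7 = 29% and, if both fell among the first six, would have met the suspension rule.

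**Illustration of sensitivity.** Let p be the true DLT rate and f the share of *all* true DLTs that this clause removes. Both are assumptions; the documents give neither. With q = p(1 − f) and 6 patients,

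P(at least 2 DLTs) = 1 − (1 − q)^6 − 6q(1 − q)^5.

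For p = 0.30 and f = 0: 1 − 0.7^6 − 6(0.3)(0.7^5) = 1 − 0.1176 − 0.3025 = 0.580.

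| p | f = 0 | f = 0.25 | f = 0.50 |
|---|---|---|---|
| 0.25 | 0.466 | 0.314 | 0.167 |
| 0.30 | 0.580 | 0.406 | 0.224 |
| 0.35 | 0.681 | 0.495 | 0.283 |
| 0.40 | 0.767 | 0.580 | 0.345 |

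**Effect on the 25% rule.** Section 11.5 points to section 11.4.2, where neither response nor progression excuses an event. Read literally, the clause does not reach the 25% rule or, through section 11.6, retreatment. But section 11.4.2 concerns management and gives no full definition of DLT; section 11.4.1 does. If the reference was meant for section 11.4.1, the exemption applies to both. The text does not settle this.

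**The case against.** The strongest reply has four parts.

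*The wording is garbled and can be read mildly.* The response limb may be a free-standing restatement of the earlier 2-week resolution test. This stands in part: the text permits the attribution and does not compel it, so an event *can* drop out, not *does*. But if *respond* meant *resolve*, the limb would add nothing to the first test. On either reading of the punctuation, a response as literally stated still exempts the event.

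*The phase is closed and the steroid problem was acted on.* DLT monitoring ended when level 2 was declared the MTD. Difficulty tapering steroids was the stated reason for moving from level 5 to level 2 and from level 2 to level -1, and level -1 was taken forward. This stands and limits the practical harm. It does not repair the reported zero count.

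*There are backstops.* Section 11.5 allows suspension for other safety concerns and requires 6-monthly review, section 11.8 has criteria based on Grade 4 events and deaths, and section 16.6 describes adverse-event review that is weekly on average. Exempted events stay in the adverse-event record. These safeguards are real, but they do not define what counts as a DLT.

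*The 25% rule is untouched as written.* This stands. A reader might infer that the exemption raises the true toxicity rate at which the 25% pause operates. The documents do not support that unless section 11.4.2 is a mistaken reference, and the counted events are not only neurological deficits.

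A reader might also take the section 11.3.3 remark that "six subjects had difficulty or remained unable to be tapered off steroids more than three months post infusion" as a guide to how many events were exempted. It is not. It describes steroid tapering in eight patients, one of them treated outside the protocol under emergency use, and reports no graded deficits.

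**Conclusion.** The point holds for the DLT definition. Section 11.4.1 contains an exemption that is weaker than the resolution test in its own bullet and weaker than the Tumor Progression bullet, and it rests on a sign that cannot separate progression from expected inflammation. A persisting Grade 3 or 4 deficit can be omitted from the count behind the level 2 MTD statement.

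The size is unknown. With 0 of 7 reported, a single re-scored event would matter; the probabilities above show direction and scale under assumed rates only. It would go too far to conclude that events were in fact exempted or that the MTD statement is wrong: no document shows either. Whether the 25% rule and retreatment monitoring are affected stays open until the section 11.5 cross-reference is resolved. The matter should be corrected, because it bears on the primary objective and the check is cheap.

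**What to change.** Reconcile four things in the protocol:
1. *respond* and *resolve* within the bullet on new neurologic deficits (section 11.4.1);
2. that bullet's route to attributing symptoms to progression and the one in the Tumor Progression bullet;
3. the 2-week window in section 11.4.1 and the 4-week window in section 11.4.2;
4. the section 11.5 reference to section 11.4.2, stating which definition feeds the 25% rule and, through section 11.6, retreatment.

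Which clinical criterion should govern is for the sponsor and investigators to decide; this review does not choose one.

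Then re-read the existing adverse-event records for level 2, levels -1 and -2, and retreatment. Report the DLT or unacceptable-toxicity counts twice: with and without the events exempted by the response clause alone. If there are none, say so; the level 2 statement is then better supported.

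The cost is a few amended sentences and a modest record review. The reported toxicity rate may look slightly less favorable.
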